2.3.2. Adverse events to Convalescent Plasma Transfusion

Adverse events to convalescent plasma will be captured and graded using two approaches:

1. CCP-related AEs will be graded using the CTCAE criteria as specified in 2.3.1
2. CCP-related AEs will also be categorized using the ISBT criteria for acute transfusion reactions including name of the reaction, and severity (Grade 1-4)

3. Analysis Sets

Given the simple nature of the outcomes it is anticipated that outcomes will be possible to collect for most individuals.

3.1. Intention to Treat Sample

The intention to treat (ITT) sample will be comprised of all patients who were randomized irrespective of whether they received the randomized intervention. That is, individuals randomized to the CCP arm who did not receive CCP would have their outcomes attributed to the CCP arm. Given the simple nature of the primary outcome we anticipate a very low rate of missing primary outcome data.

The primary analysis will be based on individuals with available outcome data and this is expected to be all patients given the simple nature of the primary outcome. For some secondary outcomes if an outcome is unknown for some individuals, analyses will be first

carried out for those with complete data (i.e. in a complete case analysis) based on a modified intention to treat sample (i.e. the intention to treat sample excluding those individuals with unknown outcome). Multiple imputation will be carried out for a sensitivity analysis in which outcome data will be generated for those where it is missing in order to approximate a true intention to treat analysis. For details of the multiple imputation procedure see Section 4.1.

3.2.Per Protocol Sample

The per protocol sample will be comprised of eligible individuals who are randomized and are treated according to the protocol. In this trial, patients will be excluded from the per protocol analysis if any of the following protocol violations occur:

- Received less than two units of CCP*
- Transfusion of second unit of CCP completed > 24 hours after randomization*
- Patient randomized to SOC but receives CCP
- Patient was randomized despite being ineligible for the trial

*special consideration will be given for instances where 1 x 500 mL unit was given

3.3.Safety Sample

The safety sample will be comprised of all randomized individuals and so will coincide with the intention to treat sample.

4. Statistical Analysis

In what follows, the analysis plans are described for the sample representing the intention to treat population. Similar analyses will be carried out for the modified intention to treat and per protocol samples.

4.1.Handling of Incomplete Data

Efforts to minimize loss-to-follow up will be considerable and we are expected to have complete data on individuals for the primary and secondary outcomes. Given the simple nature of the primary outcome it is not expected that this response will be missing. If an individual withdraws from the study early, their time to event outcomes will be censored at the time of withdrawal. For binary outcomes where data are missing, a first analysis will be based on a complete case analysis using individuals who provide information on the outcomes; this is not strictly an intention to treat analysis but rather is based on a modified intention to treat sample. There is a chance that the complete case analysis will yield biased estimates of treatment effect (Kenward and Carpenter, 2007); therefore, while there is controversy about the appropriateness of imputing outcome data in clinical trials, multiple imputation (Little and Rubin, 2002) will be used as a sensitivity analysis to enable a genuine intention to treat sample. This will involve imputing missing data via imputation models fitted to the data from individuals providing complete information. Covariates to be included in the imputation model include age, sex, key co-morbidities (e.g. diabetes, cardiovascular disease, kidney disease), treatment and the time of withdrawal from the study. Standard multiple imputation will be adopted using $m =$

50 imputed datasets with the results combined across samples and variance estimates computed based on Rubin's rules (Rubin, 1996).

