5.7. Administration

The investigational product will be administered by a bedside nurse or other clinical team member that is qualified and licensed to administer blood products. Administration date and time, will be entered into the case report form (CRF). The one (500 mL) or two (250 mL) plasma units collected from one or two donors will be considered one treatment dose.

- a. The plasma will be administered at an infusion rate of no more than 150 mL/h and a standard test dose of 50 mL/hour for the 15 minutes or as per local procedures is mandatory.
- b. If an AE develops during infusion, the infusion will be stopped and can be restarted as per investigator's decision in consultation with the bedside physician.
 - i. Most reactions to plasma are relatively minor (urticaria or volume overload) and the infusion can generally be continued. Infusion can generally be continued in cases of itching or urticarial reactions after pausing the transfusion, administering antihistamines, and observing the patient for worsening.
- c. Severe allergic reactions such as, bronchospasm and hypotension, and will require discontinuation of the infusion.
- d. Transfusion of each unit must be completed within 4 hours of removal from storage. The complete study product (either 1 x 500 mL or 2 x 250 mL) must be infused within 24 hours of randomization.
- e. No medication or solution may be added to or infused through the same tubing simultaneously, unless the solution has been approved by Health Canada for this use (i.e. normal saline).
- f. Participants must be under direct or remote observation during the first 15 minutes. Vital signs should be assessed at 15 minutes, midway through the infusion and at the end of the infusion.

The maximum tolerated dose of AFP has not been determined. The most likely adverse effect from the transfusion would be hypervolemia which may be treated with diuretics in symptomatic patients by the bedside physician. Any over-dosage needs to be reported as per section 9.10.2.

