12.4. Final Analysis Plan

The primary analysis will be based on the intention-to-treat population which will include data from all individuals who have been randomized. Outcomes will be attributed to the arm to which individuals were randomized irrespective of whether they received the planned intervention (e.g. plasma from a convalescent COVID-19 donor).

A per protocol analysis will also be performed. The per protocol sample will be comprised of eligible individuals who are randomized and are treated according to the protocol. In this trial, patients will be excluded from the per protocol analysis if any of the following protocol violations occur:

- -patient received less than two units of CCP
- -transfusion of second unit of CCP completed more than 24 hours after randomization (special consideration will be given for instances where 1 x 500 mL unit was given)
- -patient was randomized to SOC but received CCP

-patient was randomized despite being ineligible for the trial

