1.3. Sample Size Justification

Assuming a 30% risk of the composite outcome of intubation or death by Day 30 among hospitalized patients under standard of care, a sample size of 1200 individuals (800 in the CCP arm, and 400 in the standard of care arm) will provide 80% power ($\beta = 0.20$) to detect a relative risk reduction of 25% with CCP therapy using a 2-tailed test at level $\alpha = 0.05$. We assume that no patient will be lost to follow-up.

2. Responses

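### The per-protocol rules can drop CCP patients together with their early primary events while keeping comparable controls, which can tilt this supportive analysis towards CCP

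*SAP*

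**What the plan says.** SAP 3.2 lists four grounds for leaving the per-protocol sample. Two concern plasma completion: "Received less than two units of CCP" and "Transfusion of second unit of CCP completed > 24 hours after randomization". The third is receipt of CCP by a patient randomised to standard of care, and the fourth is ineligibility. Protocol 12.4 gives the same list, including "transfusion of second unit of CCP completed more than 24 hours after randomization". A footnote in the SAP promises special consideration where a single 500 mL unit was given. It sets no criteria, and there is no exception for death, intubation or a stopped infusion.

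Protocol 5.7 defines the dose differently from the unit-count rule: "The one (500 mL) or two (250 mL) plasma units collected from one or two donors will be considered one treatment dose". It also requires the complete product to be infused within 24 hours of randomisation.

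SAP 2.1 makes the day of randomisation Day 1 of the primary outcome, so events in the first 24 hours count. Protocol 12.4 makes intention to treat the primary analysis, and SAP 3.3 defines the safety sample as all randomised patients. The opening of SAP 4 says that similar analyses will be run on the per-protocol sample. Protocol 4.5 keeps patients who stop the infusion in the intention-to-treat population and says nothing equivalent for per protocol.

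**The concern.** The two completion rules select on something that happens after randomisation and that only one arm can fail. (Read literally, the fewer-than-two-units rule would also exclude every control patient, so it must be meant for the CCP arm alone.) A CCP patient who dies before the plasma is finished is removed, and the death is removed too. The same follows when deterioration leads staff to abandon the infusion or delays it past 24 hours and the patient is then intubated or dies. A control patient with the same first day stays in and counts as an event.

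This analysis will produce a relative risk reduction, a confidence interval and a p-value. If it looked favourable beside a neutral intention-to-treat result, it could be taken as the effect in properly treated patients when part of it came from the exclusion rule. Separately, the trial is open-label, so an undefined special consideration allows membership of the set to be decided with allocation and outcome known.

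**Working it through.** **Inputs from the documents.** SAP 1.3 gives the control risk ("Assuming a 30% risk of the composite outcome of intubation or death by Day 30 among hospitalized patients under standard of care"), the target effect ("detect a relative risk reduction of 25% with CCP therapy using a 2-tailed test at level" 0.05), the power ("will provide 80% power") and the arm sizes ("800 in the CCP arm, and 400 in the standard of care arm").

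**The plan's own figure first.** With 30% v 22.5%, the pooled risk is (800 × 0.225 + 400 × 0.30)/1200 = 0.25. Controls needed = [1.960 × √(0.25 × 0.75 × 1.5) + 0.842 × √(0.30 × 0.70 + 0.225 × 0.775/2)]² / 0.075² ≈ 399.1, rounded up to 400. With 800 CCP patients the total is 1200, and the power is 80.1%. The stated sample size reproduces.

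**Inputs the documents do not give (assumptions).** f is the share of CCP patients excluded for incomplete or late plasma. r is the risk of the primary outcome among them.

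**Formula, with no treatment effect and 30% risk in both arms.** All 400 controls are kept.

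- CCP risk after exclusion: p = (0.30 − f·r)/(1 − f)
- Relative risk: p/0.30
- Standard error (unpooled Wald): √[p(1 − p)/(800(1 − f)) + 0.30 × 0.70/400]
- z = (p − 0.30)/SE; rejection rate = Φ(−1.96 − z) + 1 − Φ(1.96 − z)

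**Every excluded patient has an early event (r = 100%).** For f = 2%: p = 0.28/0.98 = 0.2857; SE = √(0.2857 × 0.7143/784 + 0.000525) = 0.0280; z = −0.51.

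| f | CCP patients dropped | CCP risk | Relative risk | Two-sided rejection | Of which favouring CCP |
|---|---|---|---|---|---|
| 0.5% | 4 | 29.6% | 0.988 | 5.2% | 3.3% |
| 1% | 8 | 29.3% | 0.976 | 5.7% | 4.4% |
| 2% | 16 | 28.6% | 0.952 | 8.0% | 7.4% |
| 3% | 24 | 27.8% | 0.928 | 12.1% | 11.8% |

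The nominal values are 5% two-sided and 2.5% favouring CCP.

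**Other prognoses among those excluded, at f = 5%.**

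- r = 50%: (0.30 − 0.025)/0.95 = 0.2895, relative risk 0.965, rejection 6.6%
- r = 30%: relative risk 1.00
- r = 10%: (0.30 − 0.005)/0.95 = 0.3105, relative risk 1.035

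The direction therefore depends on whether r is above or below the average risk of 30%.

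**A rule symmetric in time.** If a share e of each arm has the event before the landmark and is excluded from both, each arm's risk becomes (0.30 − e)/(1 − e). At e = 2% that is 28.6% in both arms, so the null relative risk is 1.00.

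**What a landmark leaves behind.** A CCP patient whose infusion was abandoned for deterioration, but whose event came after the landmark, is still dropped. Assume 28% risk after the landmark and 2% of CCP patients so dropped. With later risk of 50% the relative risk is (0.28 − 0.010)/0.98/0.28 = 0.98. With later risk of 80% it is (0.28 − 0.016)/0.98/0.28 = 0.96.

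**The case against.** The strongest reply is that this is a secondary analysis. Intention to treat is primary, the safety sample is all randomised patients, and the per-protocol set has no part in alpha spending, stopping or sample size. That stands and limits the weight of the point.

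Three stronger readings are tempting, and the documents do not support them.

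- A reader might infer that any CCP patient intubated in the first 24 hours is excluded. The rules do not say so. Protocol 5.7 requires the infusion to be discontinued for severe allergic reactions, and the grounds in Protocol 4.5 do not name intubation. An intubated patient who completes plasma in time stays in, with the event counted.
- A reader might infer that the whole per-protocol set must favour CCP. Under Protocol 5.5.1 smaller Canadian sites are shipped product only after randomisation. Delays from that cause are neutral if unrelated to prognosis, and low-risk exclusions push the other way. Removing controls who received CCP would offset the bias if they were sicker.
- A reader might extend the table to f = 5% with all events, which gives a relative risk of 0.877 and 26.1% rejection. That needs 40 of 800 CCP patients, one-sixth of the 240 expected events, to have the event and fail to complete plasma, essentially within a day. Protocol 4.1.2 excludes patients already intubated, with a plan for intubation, or with a decision for no active treatment, so this is an extreme assumption.

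The single-unit conflict is also partly acknowledged: the SAP footnote attaches to both plasma rules, although Protocol 12.4 attaches the exception only to the second-unit rule. What remains is the lack of any criterion.

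None of this removes the asymmetry. No landmark, weighting or other adjustment is planned for the per-protocol analysis.

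**Conclusion.** The point holds in a limited form. The completion rules can bias the supportive per-protocol analysis towards CCP whenever the excluded CCP patients have above-average risk. The primary result is not affected.

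If 0.5% to 3% of CCP patients are dropped with early events, the null relative risk falls to between 0.99 and 0.93, and the two-sided rejection rate rises from 5% to between about 5% and 12%. At 1% or less the distortion is slight. These figures rest on assumed exclusion fractions, 30% risk in both arms, and every excluded patient having the event. The documents give neither the fraction nor the prognosis of those excluded, so the actual size and net direction cannot be determined from them. The change is worth making because it is cheap and the present rule has no safeguard.

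**What to change.** 1. In SAP 3.2 and Protocol 12.4, start the per-protocol analysis at the close of the 24-hour window in both arms, and exclude from both arms anyone who met the primary outcome before then. Outcomes are described in days, and only plasma administration is stated to have a recorded time. If event clock times are not collected, use a study-day landmark. The end of Day 2 would serve, since Day 1 is the day of randomisation.
2. State that the plasma-completion rules apply to the CCP arm only.
3. Reconcile the fewer-than-two-units rule with the Protocol 5.7 definition of one treatment dose, and replace special consideration with a written criterion fixed before outcomes by arm are examined.
4. Tabulate exclusions by arm, reason and primary outcome, and label the analysis supportive. The landmark leaves some bias from patients dropped for deterioration whose event comes later. An adherence-weighted estimate could address this.

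Items 1 to 3 need wording changes in the SAP and protocol, plus a check on which event times are recorded. The table in item 4 is small, and the weighted estimate would be an additional analysis. The statistical price is that the per-protocol estimate becomes conditional on being event-free at the landmark, so it no longer describes the effect on events in the first day.

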4.2. Analysis of Primary Outcome

If we let p_e and p_s denote the probability of the composite outcome (intubation or death at Day 30) for the experimental (CCP) and standard of care arms respectively, then the null and alternative hypotheses are $H_0: p_e = p_s$ and $H_1: p_e \neq p_s$, respectively. The probability of intubation or death between randomization and Day 30 will be estimated for each treatment group by the proportion of individuals randomized to each group who required ventilation or died by Day 30. The primary analysis will be based on a 2-sided Wald test of the null hypothesis that probability of intubation or death is the same among individuals receiving CCP or standard of care. The percent relative risk reduction, defined by $100(1 - p_e/p_s)$, will be estimated along with a 95% confidence interval.

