The study will not be commenced without the prior written approval of a properly constituted Research Ethics Board (REB), Institutional Review Board (IRB) or Independent Ethics Committee (IEC). No changes will be made to the study protocol without the prior written approval of the Sponsor and the REB, IRB or IEC, except where necessary to eliminate an immediate hazard to the subjects.

Signature Name (block letters) Title (block letters) Institution (block letters) Phone number

PROTOCOL SYNOPSIS

Title: A Randomized, Open-Label Trial of CONvalescent Plasma for Hospitalized Adults With Acute COVID-19 Respiratory Illness (CONCOR-1)

Development Phase: Phase 3

Sponsor: Hamilton Health Sciences

Study Centers: Centre Hospitalier Universitaire Sainte-Justine (CHUSJ), Montreal

(Québec Coordinating Centre); McMaster Centre for Transfusion Research, McMaster University, Hamilton (Methods Centre); University of Toronto Quality in Utilization, Education and Safety in Transfusion (QUEST) Research Program (Logistics Centre); Weill Cornell Medicine/New York-Presbyterian (New York Coordinating Centre); Hemorio (Brazilian Coordinating Centre); Meir Medical

Center, Kfar Saba, Israel (Israeli Centre)

Participating Sites Approximately 40-60 centres across Canada, one Institution in the

United States, approximately 7 centres in Brazil and one in Israel have

agreed to participate

Objective: To determine the effect of COVID-19 Convalescent Plasma at

reducing the risk of intubation or death at Day 30 in adult patients

hospitalized for COVID-19 respiratory illness.

Investigational product: Convalescent plasma from patients who have recovered from COVID-

19.

Control: Standard of care

Population: Patients ≥16 years of age (>18 years of age in the United States,

Brazil, and Israel), who admitted for COVID-19 respiratory illness and receiving supplemental oxygen for whom there is ABO-compatible COVID-19 Convalescent Plasma available. Patients are excluded if: 1) COVID-19 respiratory signs or symptoms began more than 12 days before randomization; 2) Currently intubated or a plan for intubation is in place; 3) Plasma is contraindicated (e.g. history of anaphylaxis

from transfusion); 4) Decision in place for no active treatment.

Design: Multicentre randomized open-label trial comparing COVID-19

Convalescent Plasma vs. standard of care.

Sample size: 1200 patients

Randomization: 2:1 Randomization (COVID-19 Convalescent Plasma to standard of

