1.1. Immunologic response to SARS-CoV-2

Much is still unknown concerning the immune response to SARS-Cov-2 viral infection both in normal individuals and in those that develop severe disease. A previous study of patients with severe SARS-CoV-1 infection found that recovered patients had higher and sustainable levels of both N protein-specific and S glycoprotein-specific neutralizing antibody responses compared to those who succumbed to the disease³. This suggests that antibody responses likely plays an important role in determining the ultimate disease outcome of SARS-CoV-infected patients. Immunologic senescence is also a hypothesis to explain the increased risk of complication of death or complication in the elderly population⁴.

The details of how this inappropriate humoral response translates to the severe inflammatory phenotype observed in complicating cases are still unknown⁵. One hypothesis is that inefficient clearance of virus leads to disproportionate activation of cellular and innate immunity mechanisms, similar to macrophage activation syndromes seen with viral infections in patients suffering from hemophagocytic lymphohistiocytosis. In fact, ineffective non neutralizing antibodies

against SARS-CoV-1 have been shown to worsen the inflammatory state by contributing to macrophage response activation and skewing⁶.

Most therapies currently under investigation for COVID-19 are aimed either at neutralizing the virus (e.g. remdesivir) or at preventing this disproportionate inflammatory response, with ARDS and cytokine storm (e.g. anti-IL-6). Given the suspected link between dysfunctional humoral response and COVID-19 complications, passive immunization approaches with hyperimmune products or convalescent plasma could potentially do both and constitute a promising therapeutic avenue for severe COVID-19.

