4.1.2. Exclusion Criteria

- 1. Onset of signs or symptoms of COVID-19 respiratory illness >12 days prior to randomization (eg. cough, chest pain, dyspnea, or hypoxia)
- 2. Intubated or plan in place for intubation
- 3. Plasma is contraindicated (e.g. history of anaphylaxis from transfusion)
- 4. Decision in place for no active treatment

Potential patients will be approached for informed consent. After consent is obtained, a screening ABO blood group will be collected if not already performed during the current hospital admission. Co-enrolment in other trials is allowed. For patients who fail screening, we will collect only the reason for screen failure with no personal identifiers.

Pregnant patients will not be excluded from the study if they meet eligibility criteria, except for sites where pregnant patients are not permitted to participate in the research as per local regulatory requirements. While young adults and pregnant women have been infrequently reported to present with complications, data from current COVID-19 wards indicate that those who develop severe COVID-19 pneumonia appear to have a similar risk of progression to intubation and critical disease than older patients. At the CHUM in Montreal, over half of COVID-19 patients admitted to the ICU were younger than 55 years of age. From a safety standpoint, CCP was well tolerated in one pregnant patient in a case series reported from China²¹. Therefore, based on current eligibility criteria, the same risk/benefit considerations apply to pregnant and younger patients as compared to the elderly, hence the reason not to exclude them from this trial.

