4.3. Randomization Procedures

Patients will be randomized in a 2:1 ratio (CCP to standard of care). Patients will be randomized using a secure, concealed, computer-generated, web-accessed randomization sequence. Randomization will be stratified by centre and age (<60 and ≥ 60 years). Within each stratum, variable permuted block sizes will be used. This approach will ensure that concealment of the treatment sequence is maintained.

4.4. Intervention:

Patients will be assigned to the experimental treatment (CCP) or the control (standard of care).

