12. STATISTICAL CONSIDERATIONS

12.1. Sample Size Considerations

Assuming a baseline risk of intubation or death by Day 30 of 30% in hospitalized patients with standard of care, a sample size of 1200 (800 in the CCP arm, and 400 in the standard of care arm) would provide 80% power to detect a relative risk reduction of 25% with CCP therapy using a 2-tailed test at level α = 0.05. This assumes no patient is lost to follow-up. Lost follow-up is expected to be minimal.

There is uncertainty about the intubation and mortality rate that will be observed in this study due to possibly evolving profile of COVID-19 patients admitted hospital over the course of the pandemic. To address this, a blinded sample-size re-estimation will take place when the primary outcome is available for 50% of the target sample. Sample size will only be adjusted if the estimated event rate is different than the originally specified event rate to a sufficient extent that the study is not expected to achieve the desired nominal power for the test of the primary outcome.

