12.4.1. Primary Efficacy Endpoint

Intubation or death at Day 30 is the primary endpoint.

Given the fact that the times from admission to discharge or death are expected to be relatively short, we are using a binary response indicating intubation or death at Day 30. The primary analysis will therefore be based on a 2-sided Wald test of the null hypothesis that probability of intubation or death is the same among individuals receiving CP or standard of care. The relative risk reduction for death (CCP versus standard of care) will be computed along with a 95% confidence interval.

Efforts to minimize loss-to-follow-up will be considerable and we are expected to have complete data on individuals for the primary outcome.

Sensitivity analyses will evaluate the impact of making different assumptions about missing data for secondary outcomes. These sensitivity analyses will be fully defined in the statistical analysis plan (SAP).

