4.9. Interim Calculation of Conditional Power for Futility

Conditional power will be presented as an additional guide to the IDSMC for the primary outcome based on a test for the difference in two binomial proportions (Jennison and Turnbull, 2000). Conditional power allows computation of the probability of obtaining a statistically significant result by the end of the trial given the data accumulated thus far, incorporating a hypothesized treatment effect (e.g., the treatment effect assumed for sample size determination) thereafter. If the conditional power is less than 20% under the original trial assumptions, consideration could be given to stop the trial. An unblinded independent statistician will prepare the reports for IDSMC to review when making their recommendations.

The interim analysis report will be created by an independent statistician who will have access to the randomization code.

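### The primary Wald test ignores the randomization strata (centre and age); it is valid, but a stratified relative risk would gain about 0 to 2.5 points of power at little cost

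*SAP*

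**What the plan says.** Protocol 4.3 states that "Randomization will be stratified by centre and age", with variable permuted blocks within each stratum and 2:1 allocation. The synopsis lists "Approximately 40-60 centres across Canada", one US institution, about 7 Brazilian centres and one in Israel.

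For the primary outcome, Protocol 12.4.1 says "The primary analysis will therefore be based on a 2-sided Wald test of the null hypothesis" of equal probabilities. SAP 4.2 agrees: "The primary analysis will be based on a 2-sided Wald test of the null hypothesis that probability of intubation or death is the same" in the two arms, each probability being estimated by the arm's crude proportion. Neither names a stratified or covariate-adjusted analysis, and neither says whether the Wald statistic is on the risk-difference or log relative-risk scale. Age appears only as a subgroup (Protocol 12.4.4, SAP 4.4) and as an imputation covariate (SAP 4.1).

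The protocol gives no event rates by age or centre, and its two remarks on age point in different directions. Section 1.1 mentions "the increased risk of complication of death or complication in the elderly population". Section 4.1.2 says that young adults and pregnant women who develop severe pneumonia "appear to have a similar risk of progression to intubation and critical disease than older patients".

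**The concern.** Blocking within strata forces the arms to be nearly balanced on centre and age. Outcome differences between strata then contribute little to the true sampling variation of the treatment contrast. The crude binomial variance still includes them. If the strata are prognostic, the reported standard error is too large, the interval wider than necessary, and the actual type I error below its nominal level.

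The error is on the safe side. What is at stake is precision that the design has already paid for. The antibody supplement to the SAP (section 2) already follows the same principle, since it controls for plasma provider so that comparisons are made within provider. The primary analysis does not.

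**Working it through.** **The plan's own figure.** Inputs from Protocol 12.1: control risk 30%, relative risk reduction 25% (so 22.5% with CCP), 800 v 400 patients, two-sided 0.05. Pooled risk = (400 × 0.30 + 800 × 0.225)/1200 = 0.25.

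- Null SE = √[0.25 × 0.75 × (1/400 + 1/800)] = 0.02652.
- Alternative SE = √[0.30 × 0.70/400 + 0.225 × 0.775/800] = 0.02726.
- Power = Φ[(0.075 − 1.96 × 0.02652)/0.02726] = 80.1%. The stated 80% is reproduced.
- Unpooled Wald on the risk difference: Φ(0.075/0.02726 − 1.96) = 78.6%.
- Wald on log RR: SE = √[0.70/120 + 0.775/180] = 0.1007, so Φ(0.2877/0.1007 − 1.96) = 81.5%.

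**Analytic gain.** Assume that age alone is prognostic, the two age groups are equal in size (w = 0.5), pooled risk is p = 0.25 and strata are completely balanced. With stratum risks a and b:

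- R² = w(1 − w)(b − a)²/[p(1 − p)], and s = √(1 − R²).
- True level of the crude test = 2[1 − Φ(1.96/s)].
- Crude power = Φ(0.8416/s); stratified power = Φ(2.8016/s − 1.96), where 2.8016 = 1.96 + 0.8416.
- Excess width of the crude interval = 1/s − 1.
- Extra patients for the crude test to match = 1200{[1 + 1.96(1 − s)/2.8016]² − 1}.

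For risks of 15% and 35%: R² = 0.25 × 0.04/0.1875 = 0.0533 and s = 0.9730. The level is 2[1 − Φ(2.014)] = 4.4%, and power is Φ(0.865) = 80.6% crude v Φ(0.919) = 82.1% stratified.

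| Risk by age group | R² | True level, crude | Interval excess | Power, crude to stratified | Patients |
|---|---|---|---|---|---|
| 25% / 25% | 0 | 5.0% | 0 | 80.0% to 80.0% | 0 |
| 20% / 30% | 0.0133 | 4.8% | 0.7% | 80.2% to 80.5% | 11 |
| 15% / 35% | 0.0533 | 4.4% | 2.8% | 80.6% to 82.1% | 46 |
| 12% / 38% | 0.0901 | 4.0% | 4.8% | 81.1% to 83.6% | 79 |

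**Number of strata.** 40–60 + 1 + 7 + 1 = 49–69 centres, hence 98–138 centre-by-age strata. That is 1200/138 ≈ 9 to 1200/98 ≈ 12 patients each, so blocks are often incomplete and balance is partial.

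**Simulation with incomplete blocks.** There were 10,000 trials per setting, each of 1200 patients in 59 centres (50 Canada, 1 US, 7 Brazil, 1 Israel). Unequal centre sizes and blocks of 3 or 6 were assumed. RR was 0.75, both tests were on the log RR scale, and centres with fewer than 20 patients were pooled within country. Monte Carlo SE is about 0.4 points for power and 0.2 for level.

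| Control risk by age group | Crude power | Mantel-Haenszel, age and pooled centre | Difference |
|---|---|---|---|
| 30% / 30% | 80.6% | 80.6% | 0.0 |
| 24% / 36% | 80.8% | 81.0% | +0.2 |
| 18% / 42% | 81.7% | 83.2% | +1.5 |
| 14.4% / 45.6% | 81.3% | 84.0% | +2.7 |

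The simulated level of the crude test in the three prognostic settings was 4.8%, 4.8% and 4.3%, closer to nominal than the complete-balance formula gives. Without pooling, about 21 of 1200 patients fall in strata containing one arm only, and power with no prognostic effect is 79.7%. With pooling, fewer than 1 patient is lost.

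**Varying the assumptions.** With 50 centres, age odds ratios of 1 to 4 and centre SD of 0 to 0.5 on the logit scale (4,000 trials per setting), the change in power was +0.1 to +2.2 points stratifying by age only. It was −0.6 to +1.9 stratifying by unpooled centre and age. The crude log RR test had level 4.5–4.8% with no or weak prognostic strata and 3.6% with the strongest; the centre-by-age stratified test stayed at 4.7–5.1%.

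**The case against.** The planned test is valid, and the trial was sized for it, so sizing and analysis agree. The gain is entirely assumed, and the protocol's one remark about patients with severe pneumonia suggests that age matters little, which is the end of the range where nothing is gained. All of this stands, and it is why the point is an efficiency recommendation.

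A second objection is that age alone captures the gain while centre brings the complications. When only age is prognostic this is right: 4,000 trials per setting gave 81.7% crude, 83.2% by age and 82.9% by age and pooled centre for the 18%/42% case. With a prognostic centre effect (assumed SD 0.5 on the logit scale), pooled centre added to age: 82.0% crude, 82.6% age only, 83.6% both.

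Third, more centres fall under the pooling threshold at the 600-patient interim, so the strata differ between looks. Simulating that look with its own pooling gave a type I error of 4.7%, so this is not a barrier. No figure was obtained at the 0.0054 boundary itself.

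Three qualifications stand:

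- The unnamed Wald scale moves power by about 3 points (78.6% v 81.5%), more than the stratification gain. The statement that 80% is met without the change therefore depends on the scale.
- The stratified and crude relative risk reductions are the same quantity only under a common relative risk.
- Under Protocol 11.8, changing the protocol means an amendment to regulators and ethics boards, here in four countries.

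**Conclusion.** The concern holds as a matter of efficiency. The crude test keeps type I error at or below 5%, and N = 1200 need not change. If the strata are prognostic, it gives away precision that the stratified randomization has bought: about 0 to 2.5 power points by formula (up to 2.7 in simulation), equivalent to 0 to 79 patients, with intervals 0 to 4.8% too wide. If neither factor is prognostic, nothing is gained, and with small centres pooled nothing material is lost.

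The range rests on assumed age effects corresponding to R² of 0 to 0.09, equal age groups and, in the simulation, assumed centre and block sizes. The principle is secure; the size cannot be fixed from the documents. This is a recommended improvement, not a necessary correction.

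**What to change.** Before any unblinded data are seen, amend Protocol 12.4.1 and SAP 4.2 as follows.

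1. Make the primary analysis a Mantel-Haenszel common relative risk with its stratified variance, stratified by age group and centre, tested on the log scale. This also settles the unnamed Wald scale. Modified Poisson regression with age, centre and a robust variance is an alternative, but it was not simulated here.
2. Prespecify the pooling rule, for example that centres with fewer than 20 randomized patients are pooled within country, and state that it is applied to the data available at each look.
3. Report the relative risk reduction as 100(1 − RR) from this analysis, noting that it assumes a common relative risk.
4. Use the same standardized statistic at the interim, with the levels in SAP 4.7 (0.0054 and 0.0492) unchanged. Restate conditional power in SAP 4.9, now "based on a test for the difference in two binomial proportions", for that statistic.
5. Leave the re-estimation formula in SAP 4.10 as it is; its crude variance makes it slightly conservative.
6. Keep the crude Wald test as a sensitivity analysis.

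The strata are already in the randomization system, so no further data, visits or patients are needed. The cost is the amendment, the pooling rule, the revised conditional power definition, and a few patients in one-arm strata who carry no information (fewer than 1 expected with the example rule).
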